13.2.4.2 Clinical Failure

Clinical failure is defined as failure to achieve formed stool within ≤ 3 days (72 hours) of the start of treatment with the study drug or clinical deterioration or worsening of symptoms by Study Day 5 (± 1 day, TOC/EOS Visit). The proportion of patients with clinical failure will be compared between the three treatment groups with two-sided Z tests. The significance level of these tests will be set to 0.05.

13.2.4.3 Diarrheal Syndrome

Improvement of diarrheal syndrome is defined as reduction of $\geq 50\%$ in the number of unformed stools (soft or watery) passed during a 24-hour post-enrolment interval (the intervals 0-24 hours, 24-48 hours, 48-72 hours, 72-96 hours, and 96-120 hours after the first dose of study drug) compared to number of unformed stools passed during the 24 hours immediately preceding the first dose of study drug. The proportion of patients with

improvement of diarrheal syndrome will be compared between the three treatment groups with two-sided Z tests. The significance level of these tests will be set to 0.05.

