5. Stool sample for diagnosis and culture; pre-enrollment stool form and frequency; physical examination; vital signs; clinical laboratory tests; urine pregnancy test (if appropriate); distribution and instructions on use of thermometer, electronic Patient Diary and paper Supplemental Form for documentation of concomitant medications and AEs.
6. Stool sample for diagnosis and culture; physical examination; vital signs; clinical laboratory tests; urine pregnancy test (if appropriate); AE and concomitant medication assessment. Collection of Patient Diary.

Table 9-1 Schedule of Events

Procedure	Study Day 0* Screening/ Randomization	Study Day 1*	Study Day 2	Study Day 3	Study Day 4	Study Day 5* (± 1 day) TOC/EOS	Day 30 (± 7 days) Follow-up Phone Call
Informed Consent ¹	X						
Eligibility Verification	X						
Medical History, Demographics	X						
Physical Examination ²	X					X	
Vital Signs ³	X					X	
Clinical Laboratory Tests ⁴	X					X	
Signs and Symptom Assessment of TD	X					X	
Stool Culture/Fecal Leukocytes ⁵	X					X	
Urine Pregnancy Test ⁶	X					X	
Randomization, Study Drug Dispensing	X						
Study Drug Administration ⁷		X	X	X			
Completion of Electronic Patient Diary ⁸		X	X	X	X	X	
Telephone Call to Patient				X ⁹			
Concomitant Medication Use ¹⁰	X	X	X	X	X	X	
Adverse Event Assessment ¹⁰	X	X	X	X	X	X	X ¹¹
Review of Diary/Supplemental Form				X		X	
Drug Accountability and Compliance						X	

AE=Adverse Event; EOS=End of Study; ICF=Informed Consent Form; TD=travelers' diarrhea; TOC=test of cure

- * Screening/Randomization (Study Day 0) and Study Day 1 are the same day. Study days are 24 hour periods. Study Day 1 will begin with the administration of the first dose of study drug, Study Day 2 will begin 24 hours after the administration of the first dose of study drug, and so on. Depending on the timing of the first dose of study drug, one Study Day may extend over two calendar days. Depending on the timing of the first dose, and given the window of ± 1 day for the TOC/EOS Visit, the TOC/EOS Visit can take place anywhere from Calendar Day 4 to Calendar Day 7.
- 1 Informed consent must be obtained before the patient undergoes any study-specific procedures. The Investigator must confirm that the patient is able to read and understand the language of the ICF, Patient Information, the electronic Patient Diary, and the Supplemental Form.

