9.1.2 Study Assessments

Investigators will document data from all study assessments at each visit in the electronic Case Report Form (eCRF). Patients will complete their Patient Diary daily, and their Supplemental Form as required, from the time of first administration of study drug until they return to the study facility for the TOC/EOS Visit.

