- the presence or absence and severity of enteric symptoms (abdominal pain/cramps, excessive gas/flatulence, nausea, vomiting, fecal urgency, tenesmus)
- presence or absence of any blood in stool
- body temperature.
- receive a telephone call from the study site to allow the site to:
 - determine if the patient's condition has improved.
 - confirm if the patient has noted the presence of any blood in the stool, as possibly indicative of infection with pathogens other than *E.coli*
 - confirm that patients are documenting any concomitant medications and AEs on the paper Supplement Form
 - record any concomitant medications noted in the Supplemental Form
 - record any AEs noted on the Supplemental Form
 - confirm that patients have completed the Patient Diary to date, and review Diary entries.

If a patient's condition has worsened, or if a patient has noted blood in the stool, the patient may be requested to return to the study facility. If in the opinion of the Investigator the patient requires alternate or supplemental therapy, the patient should be discontinued (Section 9.3.3), and provided with effective treatment.

9.1.2.5 Study Day 4

Study Day 4 will begin 72 hours after the administration of the first dose of study treatment. On Study Day 4, patients will complete the Patient Diary, recording:

- date, time and form of all stools passed
- the presence or absence and severity of enteric symptoms (abdominal pain/cramps, excessive gas/flatulence, nausea, vomiting, fecal urgency, tenesmus)
- presence or absence of any blood in stool
- body temperature.

Patients will document the administration of any concomitant medication or occurrence of any AEs on the (paper) Supplemental Form.

There should be no patient administration of study drug on Study Day 4. If however, study drug is administered the time and date of administration should be recorded in the Patient Diary. Any study administered as of Study Day 4 would be considered a protocol violation.

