9.1.2.6 Study Day 5 (± 1 day), Test of Cure/End of Study Visit

Depending on the timing of the first administration of the study drug, the TOC/EOS Visit may take place anywhere from Calendar Day 4 to Calendar Day 7.

Patients will complete the final entries of the Patient Diary, recording:

- date, time and form of all stools passed
- the presence or absence and severity of enteric symptoms (abdominal pain/cramps, excessive gas/flatulence, nausea, vomiting, fecal urgency, tenesmus)
- any blood in stool
- body temperature.

Patients will document the administration of any concomitant medication or occurrence of any AEs on the (paper) Supplemental Form.

Patients will also return to the study site on Study Day 5 for the TOC/EOS Visit. The following will be performed/documentated:

- physical examination, including weight and calculation of BMI
- vital signs
- clinical laboratory tests
- signs/symptoms of TD
- stool sample for culture
- urine pregnancy test, if applicable
- Investigator review of Patient Diary to ensure entries are complete
- concomitant medications noted by the patient in the Supplemental Form
- AEs noted by the patient on the Supplemental Form
- drug accountability and patient compliance check.

Once the above procedures have been carried out, patients will be considered to have completed the study. Patients with ongoing AEs on Day 5 will be followed up with a phone call on Day 30 (± 7 days); any related AE ongoing on Day 5 will be followed until the AE has resolved or until it is judged by the Investigator to be permanent (Section 12.1.4).

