11.1.2 Secondary efficacy endpoints

- TLUS defined as the interval beginning with the first dose of study drug and ending with the last unformed stool passed
- proportion of patients with clinical failure defined as failure to achieve formed stool within ≤ 3 days (72 hours) of the start of treatment with the study drug or clinical deterioration or worsening of symptoms by Study Day 5 (\pm 1 day)
- proportion of patients with improvement of diarrheal syndrome, defined as reduction of $\geq 50\%$ in the number of unformed stools (soft or watery) passed during the intervals 0-24 hours, 24-48 hours, 48-72 hours, 72-96 hours, and 96-120 hours after the first dose of study drug, compared to the number of unformed stools passed during the 24 hours immediately preceding first dose of study drug
- the number of unformed stools (soft or watery) passed during the intervals 0-24 hours, 24-48 hours, 48-72 hours, 72-96 hours, and 96-120 hours after the first dose of study drug
- the presence or absence and severity of signs and symptoms of enteric infection (abdominal pain/cramps, excessive gas/flatulence, nausea, vomiting, fecal urgency, tenesmus) – the proportion of patients with signs and symptoms of enteric infection during the intervals 0-24 hours, 24-48 hours, 48-72 hours, 72-96 hours, and 96-120 hours after the first dose of study drug
- microbiological cure defined as a post-treatment culture that was negative for the pre-treatment etiologic pathogen.

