11.2.2 Stool Frequency and Form

Patients will record in the Patient Diary the date, time and form of all stools passed, from the time of the first drug administration until the end of the study on Study Day 5 (\pm 1 day). Patients will receive detailed instructions, with diagrams, on how to rate the stool form.

Stools will be recorded as follows:

- formed (retains shape)
- soft (assumes shape of container)
- watery (can be poured).

Both soft and watery stools are to be considered unformed.

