13.2.4.4 Unformed Stools

The number of unformed stools (soft or watery) passed during the intervals 0-24 hours, 24-48 hours, 48-72 hours, 72-96 hours, and 96-120 hours after the first dose of study drug will be compared between the three groups using repeated measures Poisson regression with treatment, time, and interaction as fixed effects, and with the baseline number of unformed stools as a covariate. In the event that the data are overdispersed, a negative binomial model will be used.

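### Does the lack of a rule for a partly observed 96-120 h stool interval call for a change to the plan?

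*Protocol*

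**What the plan says.** Section 11.1.2 defines two stool endpoints over five intervals, ending with "48-72 hours, 72-96 hours, and 96-120 hours after the first dose of study drug": improvement of diarrheal syndrome (a reduction of at least half in unformed stools) and the number of unformed stools. Section 13.2.4.3 sets each interval against a full-day baseline, "compared to number of unformed stools passed during the 24 hours immediately preceding the first dose of study drug", and tests proportions with two-sided Z tests. Section 13.2.4.4 analyses the counts by "repeated measures Poisson regression with treatment, time, and interaction as fixed effects, and with the baseline number of unformed stools as a covariate", with a negative binomial model if the data are overdispersed. It names no exposure term, although the synopsis describes the analysed quantity as a rate over time.

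On timing, section 9.1.2.5 states "Study Day 4 will begin 72 hours after the administration of the first dose of study treatment", and section 9.1.2.6 adds that "the TOC/EOS Visit may take place anywhere from Calendar Day 4 to Calendar Day 7". Section 9.1.2 has patients complete the diary "from the time of first administration of study drug until they return to the study facility for the TOC/EOS Visit". Section 11.2.2 has stools recorded "from the time of the first drug administration until the end of the study on Study Day 5", with the same one-day window. Note 6 to Figure 9-1 lists, among the tasks at that visit, "AE and concomitant medication assessment. Collection of Patient Diary".

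Section 13.2.5 applies last observation carried forward to patients who discontinue early. Section 13.2 leaves the detailed description of all analyses to the SAP. SAP sections 1 and 9 limit the final analysis to safety because few patients were randomized.

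**The concern.** The last interval and the nominal visit day are the same 24 hours. A patient who complies fully and attends on Study Day 5 hands in the diary before the interval is over. This is a property of the schedule, so it affects compliant completers and not only those who drop out. The carry-forward rule does not reach them.

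If an analyst counted the stools recorded and compared that number with a 24-hour baseline, unobserved hours would be scored as stool-free. The proportion improved would be too high and the arms would be pulled together. If visit times differed by arm, the comparison would be biased. In the count model, the last time point would look lower than it was. With the rule left open, a later choice could move the reported proportion.

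**Working it through.** **1. The clock.** Study Day d covers (d-1) × 24 to d × 24 hours after first dose (section 9.1.1). Study Day 4 is therefore 72-96 h, Study Day 5 is 96-120 h and Study Day 6 is 120-144 h. An in-window visit falls at 72-144 h. Running over all clock times for the first dose, this range covers Calendar Days 4 to 7, which reproduces the protocol's own statement.

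**2. Hours observed.** For a visit at hour v, the observed part of the last interval is min(24, max(0, v - 96)).

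| Visit at (h) | 72-96 h observed | 96-120 h observed |
|---|---|---|
| 84 | 12 | 0 |
| 96 | 24 | 0 |
| 100 | 24 | 4 |
| 108 | 24 | 12 |
| 114 | 24 | 18 |
| 120 or later | 24 | 24 |

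Only a visit at 120 h or later completes the last interval. A Study Day 4 visit misses it and can shorten the one before.

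**3. Effect on one patient's improvement score, if a fragment is read as a whole day.** Assume Poisson counts. With baseline 4, improved means at most 2 unformed stools. At a true rate of 2 per 24 h, P(improved) = exp(-2) × (1 + 2 + 2) = 0.677 with full observation. With 12 h it is exp(-1) × (1 + 1 + 0.5) = 0.920, and with 4 h it is 0.995. At a true rate of 1 per 24 h, the values are 0.920 in full and 0.986 with 12 h. The difference between the two rates falls from 0.920 - 0.677 = 0.243 to 0.986 - 0.920 = 0.066.

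**4. Effect on whole arms.** Assumptions, none of them stated by the plan:
- 79% and 60% of two arms pass no unformed stools at 96-120 h. These are the cure rates for active drug and placebo in section 14.1 of the prescribing information (Appendix I).
- The remaining patients have Poisson counts at a stated multiple of their baseline rate.
- Baselines are 3 to 8, and visits are uniform over Study Day 5.

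The inflation is the share not stool-free times the rise in P(improved). At an unchanged rate the rise is 38.5-50.5 points. This gives 0.21 × 38.5 = 8.1 to 0.21 × 50.5 = 10.6 points in the first arm, and 0.40 × 38.5 = 15.4 to 0.40 × 50.5 = 20.2 in the second. At half rate the ranges are 4.5-6.6 and 8.6-12.6. At a quarter rate they are 0.9-2.3 and 1.7-4.3.

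**5. Would a written rule settle it?** Two minimum-time rules were tried. Each also keeps as non-improved any patient whose partial count already exceeds half of baseline. The entries are between-arm differences in points.

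| Handling | Unchanged rate | Half rate |
|---|---|---|
| Full interval observed (target) | 14.5-17.4 | 6.1-8.8 |
| Counted as recorded | 6.4-8.5 | 2.0-3.6 |
| At least 12 h | 12.0-15.5 | 3.9-6.8 |
| At least 18 h | 17.7-20.7 | 7.2-11.5 |

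The 12 h rule falls short of the target and the 18 h rule overshoots it. Both retain briefly observed patients according to outcome. Accepting only complete intervals avoids that bias, but drops every visit before 120 h.

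**6. Count model.** If a fraction f of the interval is observed in both arms, the expected counts are f × λ1 and f × λ2, and their ratio is still λ1/λ2. At f = 0.5 the last time effect shifts by ln(0.5) = -0.69, and the treatment ratio is multiplied by 1.00. An offset for observed hours would correct the time effect. It would not alter the treatment comparison or restore lost precision.

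**The case for a change.** The strongest case for a change is that the timing follows from the protocol alone and affects patients who do everything asked of them. The handling chosen can move the unchanged-rate difference from about 6-8 to 18-21 points, which is a reason to fix it before data are seen. The diary already holds stool dates and times, so a rule would cost only wording. The synopsis speaks of a rate while section 13.2.4.4 models interval counts.

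The timing and the missing rule stand, and so does the loose wording between the synopsis and section 13.2.4.4. The rest is weaker:

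- Section 13.2.4.3 defines improvement over a 24-hour interval, so scoring a 4-hour fragment as a day is not the natural reading. If partial intervals are non-evaluable there is no inflation, only fewer patients at the last time point. The synopsis wording already steers an analyst towards a rate for the counts.
- The largest figures need every patient who is not stool-free to be passing stools at the baseline rate on the fifth day. Section 7.1.1 gives about 4 days as the average untreated duration, and section 9.3.3 discontinues patients who worsen and need other therapy.
- The 79% versus 60% contrast is active against placebo. For the two rifaximin products, equal true rates and similar visit times leave no difference to shrink. Those cure rates are also an imperfect stand-in for stool-free, because cure in this protocol can include up to two soft stools.
- Uniform visit times are doubtful. If first dose and visit both fall within a 9-hour clinic day (an assumption), a Study Day 5 visit observes either under 9 or over 15 hours of the last interval. The behaviour of any cut-off would then differ from the table.

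**Conclusion.** The gap exists and no change follows from it. The 96-120 h interval is cut short by any in-window visit before 120 h, and the protocol gives no rule for that case. This is ordinary SAP detail that section 13.2 defers. The SAP does not supply it because it contains no efficacy analysis: last patient last visit was in April 2017 and the final analysis covers safety only. The primary endpoint does not use these intervals.

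The size depends on reading a fragment as a full day. On that reading the inflation runs from about 1-2 points (79% arm) and 2-4 points (60% arm) at a quarter of the baseline rate to about 8-11 and 15-20 at an unchanged rate, under the assumed stool-free shares, baselines 3-8, Poisson counts and uniform visit times. On the other reading the inflation is nil. The treatment ratio from the count model is unaffected if truncation is equal between arms. The minimum-time rules tried exchange one bias for another, and the choice between them rests on visit times the documents do not give. If efficacy from this design were ever analysed, the analyst would have the time-stamped diary and could define observed hours before unblinding. No result or conclusion of the trial as now planned would differ.

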13.2.4.4 Unformed Stools

The number of unformed stools (soft or watery) passed during the intervals 0-24 hours, 24-48 hours, 48-72 hours, 72-96 hours, and 96-120 hours after the first dose of study drug will be compared between the three groups using repeated measures Poisson regression with treatment, time, and interaction as fixed effects, and with the baseline number of unformed stools as a covariate. In the event that the data are overdispersed, a negative binomial model will be used.

13.2.4.5 Signs and Symptoms of Enteric Infection

The proportion of patients with the presence or absence and severity of signs and symptoms of enteric infection (abnormal pain/cramps, excessive gas/flatulence, nausea, vomiting, fecal urgency, tenesmus) during the intervals 0-24 hours, 24-48 hours, 48-72 hours, 72-96 hours, and 96-120 hours after the first dose of study drug will be compared between the three treatment groups with two-sided Z tests. The significance level of these tests will be set to 0.05.

13.2.4.6 Microbiological Cure

Microbiological cure is defined as a post-treatment culture that is negative for the pre-treatment etiologic pathogen. For those patients with a positive pre-treatment culture the proportion of patients with microbiological cure will be compared between the three treatment groups with two-sided Z tests. The significance level of these tests will be set to 0.05. This test will be considered as supportive of the similarity of populations in each arm of the study and not considered as evidence of equivalence.

13.2.5 Handling Missing Data

Patients who are discontinued early from the study due to lack of treatment effect after completing 3 days of treatment should be included in the PP population using the last observation carried forward (LOCF). Patients whose condition worsens and who require alternate or supplemental therapy for the treatment of TD should be discontinued, included in the PP population analysis using LOCF, and provided with effective treatment. Patients discontinued early for other reasons should be excluded from the PP population, but included in the mITT population, using LOCF.

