7 INTRODUCTION

7.1 Background

7.1.1 Disease epidemiology

Travelers' diarrhea (TD) may be experienced by >60% of travelers from developed countries who visit developing countries, accounting for 40,000 travelers daily or > 15 million travelers annually¹. Travelers' diarrhea is usually contracted from contaminated food or water. Bacteria, in particular enterotoxigenic *Escherichia coli* (ETEC), are the most common cause of TD. Other bacteria implicated in travelers' diarrhea include enteroaggregative *E.coli* (EAEC), *Shigella*, *Salmonella*, and *Campylobacter*. Viruses (including Rotavirus) and protozoa (*Giardia lamblia*), make up the remainder of known causes^{2,3,4}.

The average duration of untreated travelers' diarrhea is approximately 4 days, with 50% of patients being free of symptoms within 48 hours^{5,6}. In a study of 1,455 Austrian tourists, abdominal cramps were reported in just over half of all patients, less than one third of patients reported nausea and/or vomiting and 13% of patients reported fever⁶. Travelers' diarrhea tends to have a longer duration in patients with other symptoms in addition to diarrhea (suggestive of severe travelers' diarrhea) and patients in whom pathogens are identified⁷.

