11 ASSESSMENT OF EFFICACY

11.1 Efficacy Endpoints

11.1.1 Primary efficacy endpoint

The primary endpoint is clinical cure at the TOC/EOS Visit (Study Day 5 \pm 1 day). Clinical cure is defined as either:

- no stools or only formed stools within a 48 hour period and no fever, with or without other enteric symptoms, OR
- no watery stools or no more than two soft stools passed within a 24 hour period with no fever and no other enteric symptoms except for mild excess gas/flatulence.

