13.2.2 Analysis Populations

The following analysis populations will be defined for the statistical analyses:

- The Safety population will include all randomized patients who received at least 1 dose of the study product.
- The mITT population will include all randomized patients who met all inclusion/exclusion criteria, received at least 1 dose of the study drug and recorded the number of formed and unformed bowel movements during Study Day 1.
- The PP population will include all randomized patients from the mITT population who do not have a major protocol deviation that would affect treatment evaluation. Patients who discontinue the study due to lack of treatment effect after completing 3 days of treatment or whose condition worsens and who require alternate or supplemental therapy for the treatment of TD should be included in the PP population (see Section 13.2.5 for the handling of missing values).

Major protocol deviations include but are not limited to:

- lack of compliance defined as having administered <75% or >125% of the scheduled doses for the specified duration of the study
- completion of the TOC/EOS Visit outside the specified visit window (Study Day 5 \pm 1 day) (if patient did not discontinue the study due to lack of treatment effect or worsening of the underlying condition requiring alternate or supplemental therapy).

Further major protocol deviations will be defined in the SAP.

The PP population will be the primary population for establishing equivalence of rifaximin and Xifaxan regarding the primary efficacy endpoint (clinical cure). The mITT population will be the primary population for evaluation of the study sensitivity comparing the proportions of clinical cure between rifaximin and placebo and Xifaxan and placebo.

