Overall, 1257 of 2579 patients (49%) were nonresponders in the open-label phase and per the study protocol were withdrawn from the study. Other reasons for discontinuation include: patient request (5%), patient lost to follow-up (4%), adverse reaction (3%), and other (0.8%).

There were 1074 (44%) of 2438 evaluable patients who responded to initial treatment with improvement in abdominal pain *and* stool consistency. The response rate for each IBS symptom during the open-label phase of Trial 3 is similar to the rates seen in Trials 1 and 2 (see Table 7). A total of 636 patients subsequently had sign and symptom recurrence and were randomized to the repeat treatment phase. The median time to recurrence for patients who experienced initial response during the open-label phase with XIFAXAN was 10 weeks (range 6 to 24 weeks).

The XIFAXAN and placebo treatment groups had similar baseline IBS symptom scores at the time of recurrence and randomization to the double-blind phase, but symptom scores were less severe than at study entry into the open-label phase.

Patients were deemed to have recurrent signs and symptoms by the following criteria: a return of abdominal pain or lack of stool consistency for at least 3 weeks during a 4-week follow-up period. The primary endpoint in the double-blind, placebo-controlled portion of the trial was the proportion of patients who were responders to repeat treatment in both IBS-related abdominal pain *and* stool consistency as defined above during the 4 weeks following the first repeat treatment with XIFAXAN. The primary analysis was performed using the worst case analysis method where patients with <4 days of diary entries in a given week are considered as non-responders for that week.

More patients receiving XIFAXAN were monthly responders for abdominal pain *and* stool consistency in the primary analysis in Trial 3 (see Table 8).

Table 8. Efficacy Responder Rates in Trial 3 in a Given Week for at Least 2 Weeks During Weeks 3 to 6 of the Double-Blind, First Repeat Treatment Phase

	Placebo (n=308) n (%)	XIFAXAN (n=328) n (%)	Treatment Difference (95% CI¹)
Combined Responder ² : Abdominal Pain and Stool Consistency Responders ³	97 (31)	125 (38)	7% (0.9%, 16.9%)
Abdominal Pain Responders ($\geq 30\%$ reduction in abdominal pain)	130 (42)	166 (51)	9% (1.6%, 17.0%)
Stool Consistency Responders ($\geq 50\%$ reduction from baseline in days/week with loose or watery stools)	154 (50)	170 (52)	2% (-4.7%, 11.0%)

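### LOCF on the binary cure endpoint lets patients stopped for lack of effect or worsening, whose failure is already known, count as cures in the per-protocol equivalence analysis

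*Protocol*

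**What the plan says.** Protocol 11.1.1 defines a binary outcome at a fixed visit: "The primary endpoint is clinical cure at the TOC/EOS Visit", Study Day 5 ± 1 day. One route to cure needs a 48-hour window. The other is "no watery stools or no more than two soft stools passed within a 24 hour period with no fever", also with no enteric symptom beyond mild gas. Neither window is tied to a clock time relative to the visit.

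Protocol 13.2.5 then sets LOCF for three groups:

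- Patients stopped for lack of effect after three days of treatment "should be included in the PP population using the last observation carried forward (LOCF").
- Patients who worsen and need other therapy "should be discontinued, included in the PP population analysis using LOCF".
- All remaining early leavers: "Patients discontinued early for other reasons should be excluded from the PP population, but included in the mITT population, using LOCF".

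The section does not say whether cure status or diary entries are carried forward, or from which time point. Protocol 13.2.2 confirms that the first two groups belong to PP, the primary set for equivalence. It admits to mITT any eligible randomized patient who "received at least 1 dose of the study drug and recorded the number of formed and unformed bowel movements during Study Day 1".

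**The concern.** For the first two groups the reason for stopping is itself the outcome: treatment did not work. The plan keeps them in PP, where they should count against the arm they came from, but then takes their cure status from the last observation. If the last complete diary window was quiet and the worsening followed, that window can meet the 24-hour route to cure. If the withdrawal assessment takes place after rescue has begun, it can reflect the rescue. Either way a known failure may enter the equivalence comparison as a cure.

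The protocol handles the same situation explicitly elsewhere. Section 13.2.4.1 censors time to last unformed stool at 120 hours when a patient terminates early for clinical failure and the time cannot be calculated. Section 13.2.4.2 counts worsening as clinical failure. The primary endpoint has no parallel rule, so one patient could be both a clinical failure and a clinical cure.

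What is at stake is the equivalence conclusion. If more failures are converted to cures in the worse active arm, the observed difference shrinks and equivalence becomes easier to claim.

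**Working it through.** **1. The plan's own numbers.** From Protocol 13.1, with attrition as worded in the synopsis and SAP 5: 180 × 0.95 = 171 (stated 170); 90 × 0.95 = 85.5 (stated 85); 171 × 0.80 = 136.8 (stated 135). These agree to rounding, so 135 per active arm (PP) and 170/85 (mITT) are used below. Stated powers and design cure rates are redacted. The label's Study 1 rates (Appendix I, 14.1) stand in: 99/125 = 79% active and 78/129 = 60% placebo.

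**2. How few patients matter (PP).** 90% CI = d ± 1.645 × SE, with unpooled SE = √[p₁(1−p₁)/135 + p₂(1−p₂)/135]. The reference arm is set at 107/135 = 79.3%.

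| Test cures | d | 90% CI | Within ±0.20? |
|---|---|---|---|
| 90/135 | −0.126 | −0.214 to −0.038 | no |
| 91/135 | −0.119 | −0.206 to −0.031 | no |
| 92/135 | −0.111 | −0.199 to −0.024 | yes |

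In this borderline case two failures carried forward as cures reverse the conclusion. A pooled SE gives the same result: lower limits −0.215 for 90 and −0.199 for 92.

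**3. False equivalence (PP).** Take a true difference of −0.20 (test 0.59, reference 0.79). Let w be the share of an arm who are early failures and q the share of those carried forward as cured; both are assumptions. Observed rate = true rate + w × q. With d = test − reference,

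P(conclude equivalence) = Φ((0.20 − d)/SE − 1.645) − Φ((−0.20 − d)/SE + 1.645).

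Example with w = 5% reference, 10% test, q = 0.5: reference 0.79 + 0.025 = 0.815; test 0.59 + 0.05 = 0.640; d = −0.175; SE = 0.0531. The first term is essentially 1, and the second is Φ(−0.025/0.0531 + 1.645) = Φ(1.174) = 0.880, so P = 12.0%. The net shift is 135 × (0.10 − 0.05) × 0.5 = 3.4 patients.

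| w reference / test | q = 0 (scored as failures) | q = 0.25 | q = 0.5 | q = 1 |
|---|---|---|---|---|
| 5% / 5% | 5.0% | 5.0% | 5.0% | 5.0% |
| 5% / 10% | 5.0% | 7.9% | 12.0% | 25.4% |
| 10% / 5% | 5.0% | 3.0% | 1.7% | 0.4% |

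Equal misclassification has no effect, and the opposite imbalance makes the test conservative.

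**4. Other dropouts (mITT, active versus placebo, 170 v 85).** Let p be cure in completers (0.79 and 0.60) and m the dropout share, with half of dropouts quiet when last seen. Non-cure rule: p(1 − m). LOCF: p(1 − m) + 0.5m. Active, 5% dropout: 0.79 × 0.95 = 0.7505, or 0.7755 under LOCF. Placebo, 10%: 0.60 × 0.90 = 0.540, or 0.590. Placebo, 15%: 0.60 × 0.85 = 0.510, or 0.585. Power is from exact enumeration of the pooled two-sided Z test.

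| Dropout active / placebo | LOCF difference (power) | Non-cure difference (power) |
|---|---|---|
| 5% / 5% | 18.05 points (85%) | 18.05 points (83%) |
| 5% / 10% | 18.55 points (86%) | 21.05 points (92%) |
| 5% / 15% | 19.05 points (88%) | 24.05 points (97%) |

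The completer difference is 19 points. LOCF stays within 1 point of it, while the non-cure rule exceeds it by 2 to 5 points when placebo dropout is higher.

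With no drug effect (p = 0.60 in both arms) and dropout unrelated to outcome, the two-sided rejection rate under the non-cure rule is 7.6% (5%/10%) and 14.9% (5%/15%). Under LOCF it is 5.3% and 5.5%.

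LOCF is not always this neutral. If every dropout were quiet when last seen, the difference would be 0.8005 − 0.640 = 16.05 points (5%/10%) or 0.8005 − 0.660 = 14.05 points (5%/15%).

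**The case against.** Three stronger readings are tempting, and the documents do not support them.

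- **That the sentence on other early leavers biases the primary equivalence test.** It cannot, because those patients are excluded from PP. It bears only on the placebo comparisons in mITT.
- **That every patient without a test-of-cure window should be a non-cure in the main mITT analysis.** Step 4 shows that this can enlarge the active-placebo difference through dropout alone. It would also fail recovered travelers who simply move on. For this group the choice is a trade-off.
- **That the appended label sets a precedent.** Its responder analysis, "where patients with <4 days of diary entries in a given week are considered as non-responders for that week", comes from a trial in irritable bowel syndrome scored by weekly diaries, which is only a loose analogy. Likewise "with 50% of patients being free of symptoms within 48 hours" in Protocol 7.1.1 describes untreated illness and gives no rate of quiet spells among patients who stop for failure.

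The case against the narrower point is that safeguards exist. Stools are logged with date, time and form (11.2.2). The Study Day 3 call reviews the diary and asks whether the condition has improved and whether blood was seen (9.1.2.4). Section 9.3.3 seeks a full test-of-cure assessment at withdrawal. Most patients stopped for lack of effect would still be passing unformed stools, so LOCF would usually carry forward a failure. That stands, and it makes a false cure possible but not the usual result. It does not close the gap: the withdrawal visit is held only where possible, its timing relative to rescue is not stated, and no rule sets cure to no.

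Protocol 9.2 also says the statistical methodology follows the agency's guidance. That guidance is not among the documents, so whether it prescribes LOCF for cure is unknown.

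**Conclusion.** The point holds for the two groups kept in PP. Their failure is established by the reason for stopping, and the protocol leaves open that they count as cured. In the assumed scenario with more early failures on test (5% reference, 10% test), the false-equivalence rate rises from 5.0% to between 7.9% and 25.4%, depending on how many are carried forward as cured. With balanced misclassification the difference and this error rate do not change, and with the opposite imbalance equivalence becomes harder to show. The early-failure shares and q have no source in the documents, and the cure rates are label figures standing in for redacted ones.

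For other early leavers the stated LOCF rule is defensible as the main mITT analysis if its sensitivity is shown.

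A reader might infer that the trial's reported results are at risk. They are not: SAP 1 and SAP 9 remove all efficacy analyses because few patients were randomized, and SAP 8.6 plans no statistical test on safety data. The defect lies in the protocol's efficacy plan and matters if that plan is used or reused.

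**What to change.** In Protocol 13.2.5, add for clinical cure:

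- Patients discontinued for lack of effect, or for worsening that needs alternate or supplemental therapy, are classified as non-cure in both PP and mITT, whatever their last observation. PP membership and patient management do not change.
- For other early discontinuations, keep LOCF in mITT, state what is carried forward and from which window, and add a sensitivity analysis of both placebo comparisons that counts them as non-cure.

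The cost is a few sentences and one extra table. Cure rates may come out slightly lower. Before the wording is changed, the sponsor should check it against the guidance cited in Protocol 9.2. The safety-only SAP needs no change; the new wording would have to be carried into any efficacy SAP written from this protocol.
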